### 1.3 RHB-102

RHB-102 is a bimodal release oral formulation of ondansetron. It contains 24 mg of ondansetron, 6 mg immediate release and 18 mg in an extended release matrix. Pharmacokinetic studies in healthy volunteers have demonstrated rapid early release, with appearance of drug in the plasma within half an hour of dosing, similarly to immediate release Zofran®, but with sustained drug availability over 24 hours. Thus, RHB-102 should provide rapid relief from nausea and vomiting in patients not requiring immediate intravenous medication, yet require only once daily dosing for a sustained effect over the several days of illness. The safety profile of RHB-102 is similar to that of Zofran 8 mg, as demonstrated in volunteer studies.

### 1.4 Study Rationale

As noted above, ondansetron has been studied in acute gastroenteritis against placebo in seven clinical trials and against other agents in two studies. While often used clinically, its activity in adults and adolescents with acute gastroenteritis has not been demonstrated. Thus, a prospective randomized study of ondansetron in a major patient population will provide clear evidence of the efficacy of the drug, or lack thereof, in this population.

The study will of necessity enroll only those patients who are likely to tolerate oral medications. Patients with vomiting at a frequency which make it difficult for them to hold down a pill for half an hour are not appropriate for this study and will be excluded. However, for the large population of patients with moderate gastroenteritis, treatment of the disease without intravenous is clearly preferable. In addition to being easier and more comfortable even in an emergency department setting, it will allow treatment of patients outside the emergency room, providing both patient convenience and economic benefits as compared to parenteral treatments in an emergency department.

Use of a placebo control allows demonstration of activity with a reasonable sample size. Ondansetron has a very benign safety profile; one of the side effects of ondansetron, constipation, is actually a therapeutic benefit in the intended indication. In contrast, adverse events are more common with phenothiazines and metoclopramide, and they may be severe. These include dystonia and akathesia. Therefore, use of a placebo control in patients with moderate gastroenteritis may spare some patients toxicity in a situation where not all patients require pharmacologic intervention. Those patients who do require medication will promptly receive an active rescue intervention.

## **2. Objectives**

### **2.1 Primary**

Comparison of the proportion of patients who are treatment successes, i.e., fulfill all three of the following criteria: a) without further vomiting, b) without rescue medication, and c) who were not given intravenous hydration from 30 minutes after the first dose of study medication through 24 hours after the first dose of study medication.

### **2.2 Secondary**

Comparison between ondansetron and placebo groups of

- Treatment success, as defined above, through 4 days following first dose of study medication
- Proportion of patients who experience each of the components of treatment failure:
  - Vomiting
  - Rescue antiemetic therapy
  - Intravenous hydration
- Severity of nausea
- Diarrhea as reported by
  - Bristol Stool Scale (BSS): number and distribution by grade of grade  $\geq 5$  stools daily throughout the study. The Bristol Stool Scale is shown in Appendix I.
  - Stool consistency, as recorded per original protocol, none/formed (normal)/soft/watery (diarrhea)
- Incidence and severity of other symptoms of gastroenteritis
- Time from first dose of study medication to discharge from ED, extended observation unit or hospital, whichever comes last
- Time to resumption of normal activities (work/school/household)
- Proportion of patients requiring hospitalization
- Proportion of patients returning to emergency department for gastrointestinal symptoms within 4 days of initial discharge
- Adverse events

### **3. Study Population**

A total of 320 adults and children  $\geq$  age 12 with vomiting from presumed acute gastroenteritis or gastritis of  $\leq$  36 hours duration will be enrolled in this study.

#### **3.1 Inclusion Criteria**

1. Patients must have vomited at least twice in the 4 hours preceding signing informed consent.
2. A vomiting episode is defined as an episode of forceful expulsion of stomach contents. Retching if a patient has already emptied his or her gastric contents is also considered a vomiting episode. A distinct episode is characterized by a clear break in vomiting activity of at least 5 minutes. Emesis must have been nonbloody (streaks of blood presumed due to force of retching are allowed).
3. All patients (or a parent or guardian for patients  $<$  age 18) must sign informed consent. Patients  $<$  age 18 must also give assent to participate.

#### **3.2 Exclusion Criteria**

##### **1. Severe dehydration**

There is no generally accepted definition of severe dehydration in adults. As a working definition for purposes of this study, severe dehydration is defined as two or more of the following criteria in the presence of decreased intake and increased output due to vomiting or diarrhea:

- absent or severely decreased urine output,
- weak pulse and/or low blood pressure,
- parched mucus membranes,
- lethargy, confusion, delirium or loss of consciousness.

2. Signs and symptoms severe enough to require immediate parenteral hydration and/or parenteral antiemetic medication
3. Temperature  $> 39.0^{\circ}\text{C}$
4. Likely etiologies for acute vomiting and diarrhea other than acute infectious or toxic gastroenteritis or gastritis
  - a. This includes signs of an acute abdomen, which may require surgical intervention
5. Chemically-induced gastroenteritis, e.g., from alcohol, other drugs of abuse or other irritant chemicals
6. Use within 24 hours of study entry of specific medication for treatment of nausea and/or vomiting, e.g., 5-HT3 antagonists or phenothiazines, or receipt of any IV fluid for any reason. Nonspecific gastrointestinal remedies, such as antacids, proton pump inhibitors and homeopathic remedies, are permitted
7. Congestive heart failure, bradycardia, bradycardia (baseline pulse  $<$  55/min), known long QT syndrome

8. Patients who have QTc prolongation >450 msec, noted on prior or screening ECG (per standard algorithm used by institution), or who are taking medication known to cause QT prolongation  
Note: For current list of medications known to cause QT prolongation see:  
<https://www.crediblemeds.org/healthcare-providers/drug-list/>  
There are several risk categories. Use the list showing those drugs known to cause torsade de pointes (TdP).
9. Known underlying disease which could affect assessment of hydration or modify outcome of treatment, e.g., renal failure, diabetes mellitus, liver disease, alcoholism  
Patients with type 2 diabetes mellitus controlled by diet or oral medications and whose baseline blood glucose is <200 may be entered into the study
10. Abdominal surgery within the past 3 months
11. History of bariatric surgery or bowel obstruction at any time
12. Hypersensitivity or other known intolerance to ondansetron or other 5-HT3 antagonists
13. Patient has taken apomorphine within 24 hours of screening
14. Patient has previously participated in this study
15. Patient has participated in another interventional clinical trial, for any indication, in the past 30 days
16. For women of childbearing potential (WOCBP): documented or possible pregnancy. WOCBP include any female who has experienced menarche and who has not been surgically sterilized or is not postmenopausal (defined as amenorrhea  $\geq$  12 consecutive months). WOCBP are excluded if either a) they have a positive pregnancy test on screening, or b) they think they may be pregnant, even if screening pregnancy test is negative. Time since last menstrual period is not a criterion for determining pregnancy status.

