	
 
Chemically-induced gastroenteritis, e.g., from alcohol, other drugs of abuse or other irritant chemicals
 
Use within 24 hours of study entry of specific medication for treatment of nausea and/or vomiting, e.g., 5-HT3 antagonists or phenothiazines, or receipt of any IV fluid for any reason. Nonspecific gastrointestinal remedies, such as antacids, proton pump inhibitors and homeopathic remedies, are permitted.
 
Congestive heart failure, bradyarrhythmia (baseline pulse<55/min), known long QT syndrome
 
Patient who have known QTc prolongation>450 msec, noted on prior or screening ECG, or who are taking medication known to cause QT prolongation 
 
Note: For current list of medications known to cause QT prolongation see: https://www.crediblemeds.org/healthcare-providers/drug-list/ Use list showing drugs with known risk of TdP.
 
 
 
Known underlying disease which could affect assessment of hydration or modify outcome of treatment, e.g., renal failure, diabetes mellitus, liver disease, alcoholism 
 
Patients with type 2 diabetes mellitus controlled by diet or oral medications and whose baseline blood glucose is <200 may be entered into the study
 
 
 
Abdominal surgery within the past 3 months
 
History of bariatric surgery or bowel obstruction at any time
 
Hypersensitivity or other known intolerance to ondansetron or other 5-HT3 antagonists
 
Patient has taken apomorphine within 24 hours of screening
 
Patient has previously participated in this study
 
Patient has participated in another interventional clinical trial, for any indication, in the past 30 days
 
For women of childbearing potential: documented or possible pregnancy. See body of protocol for detailed definition.
 

Design	Randomized, double-blind, placebo-controlled, parallel group study

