### Notes:

aHistory, physical including VS (pulse, respiratory rate, blood pressure, temperature and, at baseline only height and weight), informed consent. For all patients: CBC with platelet count, biochemical profile and ECG. Urinalysis is required for all patients  $\geq$  age 40 and with a history of diabetes; it is optional for other patients. Blood and urine specimens should be taken expeditiously at the beginning of assessment, but patient entry into the study and treatment need not wait for lab results (other than pregnancy test and fingerstick blood glucose when required) unless clinically indicated. After phlebotomy, a saline lock may be placed so that the patient will not require an additional needle stick should he/she require intravenous fluids subsequently. History of present illness should include questioning regarding precipitating/causative factors, as well as recording of number and character of emetic and diarrheal episodes.

Patients with diet-controlled type 2 diabetes mellitus are to have a finger stick blood glucose.

For women of childbearing potential, as defined in the exclusion criteria: urine or serum pregnancy test. Negative pregnancy test result must be obtained prior to treating a patient on study.

bPatients are to be observed in the emergency department for a minimum of 4 hours after initial dose of study medication, with VS at least once every hour and recording of intake (both oral and parenteral) and number of voidings. All episodes of vomiting and diarrhea are to be recorded, and severity of nausea at baseline and every hour while in the ED noted.

All patients are to have a repeat ECG 4±0.25 hours after initial dosing with study medication. At a minimum of 4 hours after initial administration of study medication, after repeat ECG, patients may be discharged when clinically appropriate. **Any patient who has an on-study ECG showing QTc>500 msec must have a follow-up ECG showing resolution of the QTc prolongation. Timing of follow-up ECG(s) at investigator discretion. If the QTc does not decrease below 500 msec during follow-up, the medical monitor must be contacted to discuss further follow-up.**

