#### 4.6 Discontinuation of Treatment

Patients may take study medication daily for up to 4 days (day 1 medication is the one or two tablets administered in the emergency department).

- If a patient vomits or otherwise receives rescue medication in the emergency department, he or she is not to receive additional study medication, even if nausea and/or vomiting is controlled with rescue medication.
- If the QTc interval at 4 hours after initial dose of study medication is >500 msec, study medication is to be discontinued.
- Patients experiencing recurrent nausea or vomiting after discharge from the emergency department and initial discontinuation of study medication due to resolution of symptoms may opt to resume study medication.

If a patient experiences an adverse event, regardless of relationship to study medication, which, in the investigator's opinion endangers or makes it difficult to evaluate the patient, the investigator may elect to have the patient stop study medication.

If once on study, a patient requires a medication which may prolong the QTc interval, he or she should not receive further study medication. However, evaluation of the patient should continue per protocol.

Patients may elect to discontinue treatment at any time.

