#### 5.2.3 Procedures after discharge from emergency department:

Any patient who has a post-dosing ECG showing QTc>500 msec must have a follow-up ECG within 72 hours of initial dosing showing resolution of the QTc prolongation. This may be performed on an inpatient or outpatient basis at the investigator's discretion. If the QTc does not decrease below 500 msec during initial follow-up, the medical monitor must be contacted to discuss further follow-up.

If a patient vomits from 30 minutes after taking the first dose of study medication until 24 hours after the first dose of study medication or requires rescue antiemetic or parenteral hydration during that period, even without vomiting, he or she will be considered a treatment failure. In that case, the only post-emergency department follow-up will be a call 72-96 hours after discharge from the emergency department to ascertain whether the patient's symptoms have

resolved, whether any adverse events occurred, and whether the patient required further medical follow-up, either in an emergency department or other medical facility.

Prior to discharge, patients who are treatment successes (i.e., no vomiting, no rescue medication and no parenteral hydration while in emergency department) will be given a diary card to record:

- all episodes of vomiting and bowel movements, with description of each bowel movement
- severity of nausea (on a 5-point Likert scale) three times a day: before breakfast or the time at which the patient usually eats breakfast, between 1:00-2:00 pm, and at bedtime
- any symptoms the patient may have related to gastroenteritis, such as chills, fever, abdominal pain
- adverse events
- medications taken, either for gastroenteritis (study medication and others) or other conditions

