## 7.5 Safety Analyses

The safety and tolerability of RHB-102 will be determined by reported AEs, physical examinations, vital signs, and, if performed on study, laboratory tests. Subjects who receive any RHB-102 (even if they vomit shortly after administration) are considered evaluable for safety.

ECGs of patients who undergo paired ECGs on the study will be analyzed for shifts in QTCF.

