3.1. Study Design

Patients presenting to the emergency department who fulfill entry criteria will be asked to participate. A screening log will be kept listing all patients considered with reasons for patients not entering the study. Any patient whose information is reviewed in consideration for the study, even if not actually approached, is to be included in the screening log. The screening log will differentiate between those who are prescreened, i.e., who are reviewed but never progress to request for consent, from those who are screened, i.e., who are approached for consent, whether or not they actually sign consent or eventually participate in the study. Qualifying patients, once they have signed consent, will be stratified by age (\geq vs <age 18) and randomized 60:40 to RHB-102 or matching placebo. All patients will undergo laboratory testing and ECG, as specified below, once they have signed consent. Of the blood and urine tests, only results of the pregnancy test (for women of childbearing potential) and a finger stick blood glucose (for patients with type 2 diabetes mellitus controlled by diet or oral medications) are required prior to treatment. The pretreatment ECG results are available immediately and are to be used to qualify patients.

Patients will be started on oral fluids \geq 30 minutes after taking study medication (second dose for patients who receive 2 doses in ED) if they have not vomited during that period. Intravenous hydration should not be administered unless the patient has vomited or is clearly unable, after a reasonable period of time has elapsed since administration of study medication, to tolerate oral fluids.

At 4 ± 0.25 hours after initial dosing, all patients are to have a repeat 12-lead ECG. Once stable, but not less than 4 hours after initial dosing, patients may be discharged from the emergency department. On discharge, patients who are not treatment failures will be given an additional 3 doses of study medication to take at 24-hour intervals if nausea persists. Patients will be contacted daily for 4 days after discharge to determine their condition. Those patients who have persistent, worsening or recurrent nausea and/or vomiting during the follow-up period may be asked to come in for follow-up assessment by study personnel.

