9.4. Safety Analyses

The safety and tolerability of RHB-102 will be determined by reported AEs, physical examinations, vital signs, and, if performed on study, laboratory tests. Subjects who receive any RHB-102 (even if they vomit shortly after administration) are considered evaluable for safety. Physical exam findings will not be analyzed separately. Rather, new and worsening abnormalities will be considered AEs and analyzed with those data.

1) Adverse Events

The NCI-CTCAE v4.0 system will be used to grade new or worsening laboratory abnormalities. New laboratory abnormalities for which there are no CTCAE v4.0 criteria will be assigned grade 1 if there were no clinical effects or interventions, and according to the criteria in protocol section 6.3 if there were clinical effects and/or interventions. AEs will be grouped and tabulated by MedDRA preferred terms by system organ class.

The Medical Dictionary for Regulated Activities (MedDRA) version 13.1 will be used to classify all AEs with respect to system organ class and preferred term.

Summary tables of AEs and SAEs will be prepared by system organ class, preferred term and severity for each treatment group. AEs that lead to premature discontinuation from the study or to death will be listed separately via data listings.

2) Other Parameters

Findings on physical examination, including vital signs, which constitute clinically significant changes, will be listed as adverse events. The incidence of hospitalization will be compared between treatment groups as an efficacy parameter. The causes for hospitalization, other than for gastroenteritis, will be listed as SAEs.

ECGs of patients who undergo paired ECGs on the study will be analyzed for shifts in QTcF and QTcB.

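### The SAP plans only unspecified shifts in two QT corrections that diverge with heart rate, with no lead correction and no RHB-102 versus placebo estimate in the visible text

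*Protocol*

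**What the plan says.** **Analysis.** The SAP's whole visible provision for QTc is in section 9.4: "ECGs of patients who undergo paired ECGs on the study will be analyzed for shifts in QTcF and QTcB". Protocol section 7.5 uses the same sentence for one correction only: "ECGs of patients who undergo paired ECGs on the study will be analyzed for shifts in" QTcF. SAP section 9.1 says that a more detailed ECG analysis follows, but only the section 9.4 sentence does. It also says that ECGs before and 4 hours after treatment became mandatory for everyone with amendment 4, in March 2016.

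**Entry, above 450 msec.** Protocol section 3.2, exclusion 8, relies on the local reading: "noted on prior or screening ECG (per standard algorithm used by institution". The synopsis states the criterion without an algorithm: "Patient who have known QTc prolongation>450 msec, noted on prior or screening ECG". SAP section 3.1 confirms that the reading is used on the spot: "The pretreatment ECG results are available immediately and are to be used to qualify patients".

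**On study, above 500 msec.** Three statements say QTc and nothing more:
- Protocol section 4.6: "If the QTc interval at 4 hours after initial dose of study medication is >500 msec, study medication is to be discontinued".
- Notes to the Study Assessments table: "Any patient who has an on-study ECG showing QTc>500 msec must have a follow-up ECG showing resolution of the QTc prolongation".
- Protocol section 5.2.3: "Any patient who has a post-dosing ECG showing QTc>500 msec must have a follow-up ECG within 72 hours of initial dosing".

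**The concern.** The protocol treats QTc as a safety signal important enough for an entry limit, a stopping rule and mandatory follow-up. The planned analysis is thin by comparison. A shift could be a category table or a change from baseline. With two corrections and no lead, nothing says which one carries the conclusion if they disagree. The visible text also plans no treatment contrast, although a placebo arm with paired ECGs is what separates a drug effect from the course of the illness.

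The two corrections can disagree for reasons unrelated to repolarization. Bazett's and Fridericia's formulas differ by a factor that depends only on heart rate, and heart rate may change over the 4 hours between the ECGs while patients are being rehydrated.

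A smaller, separate matter is wording. Exclusion 8 delegates the correction to the institution, and the 500 msec statements do not say whether that delegation carries over. With 21 enrolling sites (SAP section 6.2.2), the same tracing could be classified differently at different sites.

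**Working it through.** The plan states no QTc figure to reproduce, so the check is how far the two named corrections can differ at the plan's own cut-offs.

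**Inputs.** The cut-offs of 450 and 500 msec are the protocol's. Heart rate at the ECG is not given anywhere and is an assumption. The range shown is 55 to 120 bpm, its lower end taken from the baseline pulse exclusion (below 55/min, exclusion 7).

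**Formulas.** With RR = 60/HR in seconds:
- QTcB = QT / RR^(1/2)
- QTcF = QT / RR^(1/3)
- Hence QTcF = QTcB × RR^(1/6)

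**Step 1: what a QTcB at the cut-off means in QTcF.**

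| HR (assumed) | RR (s) | RR^(1/6) | QTcF when QTcB = 450 | QTcF when QTcB = 500 |
|---|---|---|---|---|
| 55 | 1.091 | 1.015 | 457 | 507 |
| 60 | 1.000 | 1.000 | 450 | 500 |
| 80 | 0.750 | 0.953 | 429 | 477 |
| 100 | 0.600 | 0.918 | 413 | 459 |
| 120 | 0.500 | 0.891 | 401 | 445 |

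The corrections agree at 60 bpm. Above that QTcB is the larger, and at 55 bpm the order reverses slightly.

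**Step 2: single tracings on both sides of a cut-off, at 100 bpm.**
- QT 360 msec: QTcB = 360/0.600^(1/2) = 465 and QTcF = 360/0.600^(1/3) = 427. It is above 450 by one formula only.
- QT 400 msec: QTcB = 516 and QTcF = 474. It is above 500 by one formula only.

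The raw QT values classified differently by the two formulas run from 349 to 380 msec for the 450 cut-off and from 387 to 422 msec for the 500 cut-off. At 80 bpm they run from 390 to 409 and from 433 to 454 msec.

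**Step 3: effect on a paired change.** Hold QTcF at 400 msec and let heart rate fall from 100 to 80 bpm:
- QTcB before: 400 / 0.600^(1/6) = 435.5
- QTcB after: 400 / 0.750^(1/6) = 419.6
- Change in QTcB: −15.9 msec; change in QTcF: 0

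With QTcF held at 420 msec, the QTcB change is −16.7 msec for 100 to 80 bpm, −24.0 for 110 to 80, and −26.4 for 100 to 70. With no change in heart rate it is zero.

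**Step 4: is a treatment contrast planned elsewhere?** SAP section 7.3 calls for baseline as a covariate for continuous endpoints, but its lead sentence concerns the primary and secondary endpoints. Section 9.3 gives only descriptive statistics for continuous endpoints, and it is an efficacy section. In the visible text, neither section supplies a QTc difference between arms, and nothing calls for central reading or for one uniform calculation of QTc.

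**The case against.** The case for leaving the plan alone has several sound parts.

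- **The documents do not contradict one another.** A reader might infer that QTc carries three conflicting meanings. The text does not support that. The labels differ because the uses differ, and the SAP keeps the protocol's QTcF and adds QTcB.
- **The local algorithm at entry is a deliberate choice.** It suits a reading needed at once in an emergency department. Taking the 500 msec statements to mean the same site-read value is natural, though they do not say so.
- **QTcB would not conceal a drug effect.** A reader might infer that it would. But QTcF is reported beside it, so in step 3 the reader would see QTcF unchanged. Slowing common to both arms would also largely cancel in a comparison with placebo. An artefact would remain only if heart-rate change differed by arm, which is conceivable if one arm's vomiting is better controlled, but the documents give no data on it.
- **Heart rates are assumed.** Exclusion of severe dehydration, of patients needing immediate parenteral hydration and of temperature above 39.0°C limits how fast these patients are likely to be.
- **Some text is not visible.** Section 5 of the supplemental SAP is among the parts not available, so an ECG provision there cannot be ruled out.

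All of this stands, and it narrows the point. It does not supply a lead correction or a between-arm estimate. The cancellation argument itself depends on a comparison with placebo, which the visible text does not plan.

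**Conclusion.** The point holds as a low-cost improvement to a secondary safety analysis. In the visible text, unspecified shifts in two corrections are weaker than the paired ECGs and the randomized control allow. The gap between corrections is zero at 60 bpm. At 100 bpm it is 37 msec at the 450 cut-off (450 − 413) and 41 msec at the 500 cut-off (500 − 459). A paired QTcB change can move by about 16 msec with QTcF constant. All three non-zero figures rest on assumed heart rates.

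Separately, the synopsis and the three 500 msec statements leave open whether the institution's algorithm in exclusion 8 applies. A reader might infer that entry and stopping did differ by site. The documents support only that they could have differed: they do not say which algorithms sites used or that sites used different ones. The number of patients affected therefore cannot be computed.

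The primary efficacy test and the sample size are unaffected. The only link to efficacy is that Subgroup Population 1 requires the entry criteria to be met.

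**What to change.** **Analysis.** For patients with paired ECGs:
1. Compute QTcF by one formula from the recorded QT and heart rate, and make it the lead measure, in line with protocol section 7.5.
2. Report the RHB-102 minus placebo difference in change from baseline QTcF, adjusted for baseline QTcF, with a 95% CI.
3. Keep QTcB as supportive.
4. State how many patients in each arm have both ECGs, because they were required of everyone only from amendment 4.

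The supplemental SAP gives June 3, 2017 as the unblinding date, so this must be labelled as a supplementary analysis, not a prespecified one.

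**Wording.** Reconcile the synopsis criterion, exclusion 8, section 4.6, the Study Assessments notes and section 5.2.3, so that each says which QTc it means. Which definition governs entry, stopping or follow-up is a clinical decision, and none is proposed here. At this stage the clarification serves the study report and any later protocol.

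**Cost.** One extra analysis and a few lines of text, with no new ECGs. This assumes that QT and heart rate are recorded or can be retrieved; the plan to report both QTcF and QTcB suggests so.
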